4.1.2 Exclusion Criteria

Patients who meet any of the following criteria will be excluded from study entry:

Exclusions Related to GPA or MPA

- Diagnosis of Churg-Strauss syndrome, as defined by the Chapel Hill Consensus Conference ([Jennette 1994](#); see [Appendix 6](#))
- Limited disease that would not normally be treated with CYC
- Severe disease requiring mechanical ventilation due to alveolar hemorrhage
- Requirement for plasmapheresis or dialysis at screening

Exclusions Related to General Health

- Incomplete recovery from recent surgery or < 12 weeks since surgery prior to baseline or planned within 24 weeks of baseline
- Lack of peripheral venous access
- Pregnancy or breastfeeding
- Evidence of 1) other significant uncontrolled concomitant disease, including, but not limited to, cardiovascular disease, nervous system, pulmonary, renal disease (including anti-glomerular basement membrane [GBM] disease); or 2) hepatic, endocrine, or gastrointestinal disorders that, in the investigator's opinion, would preclude or interfere with patient participation
- Primary or secondary immunodeficiency (history of or currently active), including known history of human immunodeficiency virus (HIV) infection
- Evidence of active tuberculosis (patients receiving chemoprophylaxis for latent tuberculosis infection are eligible for the study) (see Section 4.5.6.1)
- Known active infection of any kind (excluding fungal infections of nail beds), or any major episode of infection requiring hospitalization or treatment with IV anti-infective agents within 4 weeks of baseline or completion of oral anti-infective agents within 2 weeks prior to baseline

Entry into this study may be reconsidered once the infection has fully resolved

- History of deep space/tissue infection (e.g., fasciitis, abscess, osteomyelitis) within 24 weeks prior to baseline
- History of serious recurrent or chronic infection
- History of cancer, including solid tumors, hematologic malignancies, and carcinoma in situ (except basal cell and squamous cell carcinoma of the skin that have been excised and cured)
- Currently active alcohol or drug abuse or history of alcohol or drug abuse

Exclusions Related to Medications

- History of a severe allergic or anaphylactic reaction to a biologic agent or known hypersensitivity to any component of rituximab or to murine proteins
- Treatment with rituximab or other biologic B cell-targeted therapy (e.g., anti-CD19, anti-CD20, anti-CD22, or anti-B-lymphocyte stimulator [BLys]/BAFF) within 6 months prior to baseline visit
- Previous treatment with an anti-alpha 4 integrin antibody or co-stimulation modulator
- Previous treatment with other cell-depleting therapies, including, but not limited to, investigational agents (e.g., alemtuzumab [CAMPATH[®]], anti-CD4, anti-CD5, anti-CD3, and anti-CD11a)
- Receipt of oral or IV CYC within the previous 4 months prior to the baseline visit
- Receipt of infliximab within the previous 3 months prior to the baseline visit

- Receipt of adalimumab within the previous 2 months prior to the baseline visit
- Receipt of etanercept within the previous 1 month prior to the baseline visit
- Treatment with any investigational agent within 28 days of baseline or 5 half-lives of the investigational drug (whichever is longer)
- Receipt of any live or attenuated vaccine within 28 days prior to baseline
 - It is recommended that a patient's vaccination record and the need for immunization should be carefully reviewed and updated prior to receiving rituximab (see Section 4.4.3).
- Intolerance or contraindications to IV glucocorticoids

In case of receipt of any other immunosuppressant therapy (apart from corticosteroids), contact the Sponsor.

Exclusions Related to Laboratory Findings

- Positive serum human chorionic gonadotropin measured at screening or a positive pregnancy test prior to the first rituximab infusion for participants of childbearing potential
- Positive tests for hepatitis B surface antigen (HBsAg), hepatitis B core antibody (HBcAb), hepatitis B virus (HBV), or hepatitis C serology
- Level of IgM below LLN of age-specific reference range
- *Level of IgG below 5.65 mg/ml*
- Absolute neutrophil count (ANC) $< 1.5 \times 10^3/\mu\text{L}$
- Platelet count $< 130 \times 10^3/\mu\text{L}$
- Estimated GFR $< 15 \text{ mL/min/1.73 m}^2$ (calculated using the Schwartz formula; see Appendix 3)
- Alanine aminotransferase (ALT) or aspartate aminotransferase (AST) levels $> 2.5 \times$ the upper limit of normal (ULN) (for age and sex) that cannot be attributed to underlying GPA or MPA

4.2 METHOD OF TREATMENT ASSIGNMENT AND BLINDING

This is an open-label study. All eligible patients will be assigned to receive rituximab treatment.

4.3 STUDY TREATMENT

Treatment	
Investigational medicinal products	
Test product	Rituximab
Comparator	Not applicable
Non-investigational medicinal products	
Comparator	Not applicable
Background therapy	Prednisone, prednisolone, and methylprednisolone
Premedication	Paracetamol/acetaminophen and antihistamine cetirizine hydrochloride (or similar)

4.3.1 Formulation, Packaging, and Handling

4.3.1.1 **Rituximab (Investigational Medicinal Product)**

The rituximab drug product is manufactured from bulk drug substance by Genentech (US License No. 1048). Study drug packaging will be overseen by the Roche Clinical Trial Supplies Department and will bear a label with the identification required by local law, the protocol number, drug identification, and dosage.

The packaging and labeling of the study drug will be in accordance with Roche standards and local regulations. Study drug must be stored according to the details on the product label. The drug label indicates the storage temperature. Local packaging in some countries may be different.

Upon arrival of investigational products at the site, site personnel should check for damage and verify proper identity, quantity, integrity of seals, and temperature conditions, and report any deviations or product complaints to the monitor upon discovery.

Rituximab is a sterile, clear, colorless, preservative-free liquid concentrate for IV administration. The product is supplied at a concentration of 10 mg/mL in either 100-mg (10-mL) or 500-mg (50-mL) single-use vials. Rituximab is formulated for IV administration in sodium chloride 9 mg/mL, sodium citrate dihydrate 7.35 mg/mL, polysorbate-80 0.7 mg/mL, and sterile water for infusion. The pH is adjusted to 6.5. The vials provided to the pharmacy will have study-specific investigational agent labels. Rituximab vials are stable at 2°C–8°C (36°F–46°F) and have a proposed shelf life of 30 months. Once reconstituted into IV bags, rituximab is chemically stable for up to 24 hours at 2°C–8°C (36°F–46°F). Rituximab vials should be protected from direct sunlight.

4.3.1.2 **Background Therapy (Non-Investigational Medicine Product)**

For additional details, see the local prescribing information for IV methylprednisolone and oral prednisolone or prednisone.

4.3.2 Dosage, Administration, and Compliance

4.3.2.1 Rituximab (Investigational Medicinal Product)

4.3.2.1.1 Dosage and Administration

For this trial, rituximab will be given as an IV infusion of 375 mg/m² once a week for 4 consecutive weeks, starting at the baseline visit. The dose for rituximab will be calculated according to the participant's BSA at the screening visit after the participant's eligibility has been established, and it will remain the same for all four infusions. Each participant's actual body height and weight, measured during the 28-day period before baseline (i.e., during the 28 days before the start of administration of open-label rituximab) will be used to calculate a patient's BSA according to the Dubois formula ([DuBois and Dubois 1916](#)):

$$\text{BSA (m}^2\text{)} = [(\text{Weight in kg})^{0.425} \times (\text{Height in cm})^{0.725}] \times 0.00718$$

Note: Do not round until the end of the calculation.

4.3.2.1.2 Preparation

Use appropriate aseptic technique in preparing rituximab for administration. Withdraw the necessary amount of rituximab and dilute to a final concentration of 1–4 mg/mL into an infusion bag containing 0.9% sodium chloride USP *or* British Pharmacopoeia. The investigator may prescribe a concentration of 4 mg/mL for volume-sensitive participants. Gently invert the bag to mix the solution. Discard any unused portion left in the vial. Parenteral drug products should be inspected visually for particulate matter and discoloration before administration. Reconstituted rituximab is stable at 2°C–8°C (36°F–46°F) for 24 hours. No incompatibilities between polyethylene bags have been observed. However, because rituximab solution does not contain a preservative, diluted solution should be stored refrigerated (2°C–8°C).

4.3.2.1.3 Pre-Infusion Medication

Patients should be medicated pre-infusion with paracetamol/acetaminophen and cetirizine hydrochloride (or similar antihistamine), both according to labeled age-related doses, to be given 1 hour (± 15 minutes) before each infusion of rituximab. Subject to investigator's discretion, corticosteroid premedication with an IV infusion of 100 mg of methylprednisolone may be administered at least 30 minutes prior to infusion of rituximab (but not prior to clinical assessments) if the patient has experienced an IRR with a previous rituximab infusion.

4.3.2.1.4 Monitoring

Facilities for immediate emergency intervention, including resuscitation in case of an anaphylactic reaction, must be available. Vital signs (i.e., pulse rate, systolic and diastolic blood pressure, and temperature) will be taken pre-infusion. During the infusions, vital signs will be assessed every 15 minutes for 1 hour, then every 30 minutes, and at least 1 hour after the completion of the infusion. A physician will be available on site. Rituximab must not be administered as an IV push or bolus because

hypersensitivity reactions may occur. After infusion, the IV line should remain in the participant for at least 1 hour to enable the administration of drugs, if necessary. The participant's vital signs must be checked 1 hour after the infusion. For additional information, see [Appendix 7](#).

4.3.2.1.5 Assessment of Compliance

Accountability and patient compliance will be assessed by maintaining adequate drug dispensing and return records. A call for drug administration to the interactive voice/web-based response system (IxRS) will also be used to assess compliance.

Guidelines for dosage modification and treatment interruption or discontinuation are provided in Section [5.2.3](#).

4.3.2.1.6 Destruction of the Investigational Medicinal Product

Local or institutional regulations may require immediate destruction of used investigational medicinal product (IMP) for safety reasons. In these cases, it may be acceptable for investigational site staff to destroy dispensed IMP before a monitoring inspection, provided that source document verification is performed on the remaining inventory and reconciled against the documentation of quantity shipped, dispensed, returned, and destroyed. Written authorization must be obtained from the Sponsor at study initiation before destruction.

If there are any issues with the drug, it should be returned to the appropriate Roche Clinical Trial Supplies Department for long-term storage and not be destroyed.

Written documentation of destruction must contain the following:

- Identity (batch numbers and patient identification numbers) of destroyed IMP
- Quantity of IMP destroyed
- Date of destruction
- Method of destruction
- Name and signature of responsible person who destroyed the investigational products

4.3.2.2 Methylprednisolone (Non-Investigational Medicinal Product)

4.3.2.2.1 Dosage, Administration, and Compliance

Patients must receive three daily doses of 30 mg/kg of methylprednisolone (up to 1 g/day) or the equivalent dose of other glucocorticoids by IV infusion, which can occur at any time, up to and including Day 1. If clinically indicated, and at the discretion of the investigator, additional doses (up to three) of methylprednisolone (30 mg/kg, up to 1 g/day, or equivalent) can be given by IV infusion. No more than six doses of methylprednisolone in total may be given. All methylprednisolone doses must be completed prior to the first rituximab infusion.

The first rituximab infusion must occur no longer than 14 days after the final IV glucocorticoid dose; the final IV glucocorticoid dose may be given on Day 1 (prior to the first rituximab infusion).

Compliance will be assessed according to completion of a glucocorticoid log.

4.3.2.3 Prednisolone or Prednisone (Non-Investigational Medicinal Product)

4.3.2.3.1 Dosage, Administration, and Compliance

On Day 1 and following completion of IV glucocorticoids, all patients will receive concomitant oral prednisolone or prednisone (1 mg/kg/day or up to 60 mg/day or equivalent, whichever is lower), the dose of which will be tapered to a minimum of 0.2 mg/kg/day (or 10 mg/day, whichever is the lowest) no later than Month 6.

The general guidance on the suggested oral steroid dose-tapering schedule is to taper from 1 mg/kg/day (60 mg/day, maximum) at the start of treatment, to 0.8 mg/kg/day by Month 1, and then by 0.1–0.2 mg/kg/day each month to 0.2 mg/kg/day (or 10 mg/day, whichever is the lowest), which should be reached no later than Month 6.

Oral prednisone (used in some non-UK sites) may be substituted for prednisolone at the same dose as long as there is no hepatic impairment.

The steroid-tapering practice is specific to a particular patient and as such should be tailored individually for each patient at the time of study entry, at the discretion of the investigator.

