3.1.2 Remission Induction Phase

Prior to the first rituximab infusion, patients must receive three doses of methylprednisolone at 30 mg/kg/day (up to 1 g/day) by IV infusion that can occur any time after screening, up to and including Day 1. If clinically indicated, and at the discretion of the investigator, additional daily doses (up to three) of methylprednisolone (30 mg/kg, up to 1 g/day) can be given by IV infusion. No more than six doses of methylprednisolone in total can be given. All methylprednisolone doses must be completed prior to the first rituximab infusion. The first rituximab infusion must occur no later than 14 days after the last dose of methylprednisolone infusion. Subject to the investigator's discretion, corticosteroid premedication with an IV infusion of 100 mg of methylprednisolone may be administered at least 30 minutes prior to the infusion of rituximab (but not prior to clinical assessments) if the patient has experienced an IRR with a previous rituximab infusion.

Rituximab will be administered to patients as four weekly IV infusions of 375 mg/m² on Days 1, 8, 15, and 22. The dose will be calculated using a patient's body surface area (BSA) at screening. Infusions can be given in a day care or inpatient setting. It is acceptable to hospitalize a patient as per local clinical practice. All patients will receive concomitant oral prednisolone or prednisone (maximum, 1 mg/kg/day or up to 60 mg/day, whichever is less), which will be tapered to a minimum of 0.2 mg/kg/day (or 10 mg/day, whichever is lowest) no later than by Month 6. Following completion of rituximab infusions on Day 22, patients will complete study visits at Months 1, 2, 4, and 6 and will undergo assessments in accordance with the schedule of assessments (see [Appendix 1](#)). For more details about rituximab administration, pre-infusion medications, and monitoring of patients during infusion, see [Section 4.3.2](#).

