Appendix 1 Schedule of Assessments (cont.)

- ^a For visit windows, please refer to [Appendix 2](#).
- ^b The screening visit must be completed within 28 days of the baseline visit.
- ^c Assessments performed within 14 days of the baseline visit do not have to be repeated at the discretion of the investigator and if not clinically indicated.
- ^d Until the common closeout date.
- ^e At the common closeout date, patients whose *peripheral* B cells remain depleted, will continue to attend study visits every 3 months until their *peripheral* B-cell counts have returned to *pre-rituximab* baseline levels or to within the normal range for the population, whichever is lower.
- ^f Three times daily IV infusions of 30 mg/kg of methylprednisolone (up to 1 g/day, or equivalent) may be administered at any time, up to and including Day 1 (prior to the first rituximab infusion). If clinically indicated, and at the discretion of the investigator, an additional three daily doses of methylprednisolone (up to 1 g/day) can be given by IV infusion. No more than six doses in total can be given. All doses must be completed prior to the first rituximab infusion. The first rituximab infusion must occur no later than 14 days after the last dose of methylprednisolone infusion.
- ^g All patients will receive concomitant oral prednisolone or prednisone (1 mg/kg/day; up to 60 mg/day, or equivalent), which will be tapered to a minimum of 0.2 mg/kg/day (or 10 mg/day, whichever is lower) no later than Month 6.
- ^h Patients should be premedicated with paracetamol/acetaminophen and cetirizine hydrochloride (or similar antihistamine), both according to labeled age-related doses, to be given 1 hour (\pm 15 minutes) before each infusion of rituximab.
To be completed for female patients of childbearing potential.
- ⁱ After screening, only if clinically indicated.
- ^j Vital signs should be taken immediately prior to infusion. During an infusion, record vital signs every 15 minutes for 1 hour; then every 30 minutes; and then at least 1 hour after the completion of the infusion.
- ^k To be completed at screening and, if normal, only if indicated thereafter. If the chest X-ray is abnormal, repeat at Month 1 and as indicated thereafter.
- ^l CT scan to be completed only if indicated.
- ^m Within the last 365 days of the screening visit
- ⁿ [REDACTED]
- ^o [REDACTED]
- ^p CD19 B-cell samples to be obtained prior to infusion of rituximab
- ^q [REDACTED]
- ^r [REDACTED]

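### Used every month, the lowest step of the suggested oral steroid taper misses the protocol's own Month 6 deadline (minor; reconcile the wording)

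*Protocol*

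**What the plan says.** Protocol Section 4.3.2.3.1 contains a rule and a suggested way of meeting it.

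- **The rule.** All patients start at 1 mg/kg/day with a 60 mg/day ceiling, and the dose is to be "tapered to a minimum of 0.2 mg/kg/day (or 10 mg/day, whichever is the lowest) no later than Month 6".
- **The suggestion.** "The general guidance on the suggested oral steroid dose-tapering schedule" is to "taper from 1 mg/kg/day (60 mg/day, maximum) at the start of treatment", then "to 0.8 mg/kg/day by Month 1, and then by 0.1–0.2 mg/kg/day each month to 0.2 mg/kg/day" (or 10 mg/day if lower), a target "which should be reached no later than Month 6".

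The synopsis, under Prednisolone or Prednisone, repeats both. The deadline without the step sizes also stands in the synopsis account of the induction phase, in Protocol Section 3.1.2 ("tapered to a minimum of 0.2 mg/kg/day (or 10 mg/day, whichever is lowest) no later than by Month 6"), in footnote g of Protocol Appendix 1 ("which will be tapered to a minimum of 0.2 mg/kg/day (or 10 mg/day, whichever is lower) no later than Month 6") and in footnote g of SAP Appendix 2. Section 4.3.2.3.1 ends by leaving the taper to be adapted to each child by the investigator.

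**The concern.** The suggested schedule gives a dose at Month 1, a range of monthly reductions and an end date. A reader would expect any step inside the range to arrive by the end date. The smallest one does not.

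This is the text a site will use when it plans a child's taper at study entry. A site that takes the lowest step every month finds at the Month 6 visit that the child is above the required dose. The result is an avoidable deviation and some extra steroid exposure at the end of induction. SAP Section 4.1 summarises major protocol deviations in that phase, and SAP Section 5.1 reports steroid exposure for it and steroid use at Month 6.

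**Working it through.** **Inputs** (Protocol Section 4.3.2.3.1 and synopsis): 0.8 mg/kg/day at Month 1; monthly step s between 0.1 and 0.2 mg/kg/day; target at Month 6 equal to the lower of 0.2 mg/kg/day and 10 mg/day; starting ceiling 60 mg/day. Body weights below are assumptions; the documents give none.

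**Reading A: 0.8 at Month 1, first further step at Month 2.** Dose at Month m = 0.8 − s × (m − 1), held at 0.2 once reached.

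- s = 0.10: Months 1 to 7 are 0.8, 0.7, 0.6, 0.5, 0.4, 0.3, 0.2. The Month 6 dose is 0.3, which is 50% above 0.2.
- s = 0.12: 0.2 is reached at Month 6.
- s = 0.15: 0.2 is reached at Month 5.
- s = 0.20: 0.2 is reached at Month 4.
- Four steps of 0.1 and one of 0.2: 0.8 − 0.4 − 0.2 = 0.2 at Month 6.

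So the stated Month 6 figure is reproduced for steps of 0.12 and above, and not for 0.10. The implied average is (0.8 − 0.2)/5 = 0.12 mg/kg/day per month.

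**Reading B: 0.8 in place before Month 1, first 0.1 step taken at Month 1.** Six steps fit: 0.8 − 6 × 0.1 = 0.2 at Month 6. The mg/kg target is met exactly.

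**The absolute limit.** 10 mg/day is the lower target once 0.2 × weight exceeds 10, that is, above 10/0.2 = 50 kg. At the 0.1 step throughout:

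| Assumed weight | Month 6 target | Reading A (0.3 × weight) | Reading B (0.2 × weight) | Average step implied, Reading A |
|---|---|---|---|---|
| 20 kg | 4 mg | 6 mg | 4 mg | 0.12 |
| 50 kg | 10 mg | 15 mg | 10 mg | 0.12 |
| 60 kg | 10 mg | 18 mg | 12 mg | (48 − 10)/5/60 = 0.127 |
| 75 kg | 10 mg | 22.5 mg | 15 mg | (60 − 10)/5/75 = 0.133 |

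Reading B therefore rescues the low step up to 50 kg but not above it. Beyond 75 kg the 60 mg ceiling fixes the Month 1 dose (0.8 × 75 = 60), and the gap narrows. It closes at (60 − 10)/(6 × 0.1) = 83.3 kg on Reading B and (60 − 10)/(5 × 0.1) = 100 kg on Reading A.

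The implied averages are a consistency check, not a proposed regimen.

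**The case against.** The schedule is offered as guidance and is to be adapted to each child. The deadline stands in the same sentence and, separately, as a rule for everyone, so it can fairly be read as limiting which steps are usable. Most of the range meets it. All of this stands, and it is why the point is minor. It does not remove the mismatch, because nothing in the text tells a site that the lowest step cannot be used throughout.

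Four stronger conclusions are tempting, and the documents do not support them.

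- **That the step range, the Month 1 figure and the deadline cannot all hold.** They can: any average step of about 0.12 or more satisfies all three below 50 kg, and 0.127 does so at 60 kg. Both lie inside the stated range.
- **That a compliant site could miss the target.** A site still at 0.3 mg/kg/day at Month 6 has missed an explicit rule, whatever step it used. It followed the suggested step, not the protocol as a whole.
- **That the Month 1 figure contradicts the ceiling at 75 kg.** There 0.8 mg/kg equals 60 mg, so the Month 1 figure is already met at the start. That is how a ceiling works.
- **That children would fail a steroid condition in the Month 6 remission endpoint.** The efficacy definitions are blacked out, and no steroid threshold for remission is visible. Protocol Section 4.4.4 attaches failure to prohibited therapy, or to disease treatment other than the protocol's glucocorticoids, and names no dose. Section 4.4.1 permits other glucocorticoids.

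A complaint that sites using different steps would not be comparable at Month 6 also fails as an argument for this change: the flexibility is deliberate and would survive any rewording.

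**Conclusion.** A real but minor numerical inconsistency in dosing guidance. With 0.8 mg/kg/day at Month 1 and the lowest step every month, the Month 6 dose is 0.3 against 0.2 mg/kg/day, and the target is reached one month late. Between 50 kg and about 83 kg the low step also misses the 10 mg/day limit if the first step is moved to Month 1.

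The result rests on one step per month, a constant 0.1 step and assumed weights. The mg/kg shortfall depends on Reading A, which is the natural one; the shortfall above 50 kg does not.

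The study is descriptive, with safety and PK as primary objectives and no hypothesis testing. No sample-size statement or visible endpoint depends on the taper step. What is at stake is avoidable Month 6 deviations and some added steroid exposure.

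**What to change.** Reconcile the step range, the Month 1 figure and the Month 6 target in Protocol Section 4.3.2.3.1 and in the matching synopsis paragraph, so that the suggested schedule and the deadline agree across the whole stated range. Say when the first step after 0.8 mg/kg/day is meant to fall, and check the result for children above 50 kg, where the 10 mg/day limit is the lower target. Which figure or wording changes is a clinical decision for the sponsor and investigators.

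If the deadline itself is left alone, Protocol Section 3.1.2 and the two schedule footnotes need no change. The cost is wording in two places, with no new data, patients or analyses.
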